2.1.3 Other objectives

- To assess the dose change in use of concomitant medications in study participants receiving rozanolixizumab
- To assess the plasma concentrations of rozanolixizumab administered by subcutaneous (sc) infusion
- To assess the pharmacodynamic effects of rozanolixizumab as measured by IgG levels, IgG subclasses and MG-specific autoantibodies levels
- To evaluate the incidence and emergence of anti-drug antibodies (ADAs) with respect to immunogenicity, pharmacokinetic (PK), and pharmacodynamics
- To assess the effect of rozanolixizumab on biomarkers including IgM, IgA, and IgE, serum and plasma complement levels, and serum cytokines
- To assess the effect of rozanolixizumab on tetanus IgG antibodies

2.2 Study endpoints

2.2.1 Safety endpoints

2.2.1.1 Primary safety endpoints

- Occurrence of treatment-emergent adverse events (TEAEs)
- Occurrence of TEAEs leading to permanent withdrawal of study medication

2.2.1.2 Other safety endpoints

- Occurrence of adverse events of special monitoring (AESMs)
- Vital sign values and changes from Baseline (systolic and diastolic blood pressure and pulse rate)
- 12-lead electrocardiogram (ECG) values and change from Baseline at each scheduled assessment
- Clinical laboratory findings (hematology, biochemistry, and urinalysis)

2.2.2 Efficacy endpoints

2.2.2.1 Secondary efficacy endpoints

- Change from Baseline in MG-Activities of Daily Living (MG-ADL) at each scheduled assessment during Treatment and Observation Periods
- Change from Baseline in MG-Composite (MG-C) score at each scheduled assessment during Treatment and Observation Periods
- Change from Baseline in Quantitative Myasthenia Gravis test (QMG) at each scheduled assessment during Treatment and Observation Periods
- Use of rescue medication (intravenous infusion of immunoglobulin G [IVIg] or plasma exchange [PEX]) (Y/N)

2.2.2.2 Other efficacy endpoints

- Change from Baseline in MG Impairment Index (MGII) total scores at each scheduled assessment during Treatment and Observation Periods
- Change from Baseline in MGII ocular subscores at each scheduled assessment during Treatment and Observation Periods
- Change from Baseline in MGII generalized domain subscores at each scheduled assessment during Treatment and Observation Periods
- Change from Baseline in the MG Symptoms Patient-Reported Outcome (PRO) 'Muscle Weakness Fatigability' score at each scheduled assessment during Treatment and Observation Periods
- Change from Baseline in the MG Symptoms PRO 'Physical Fatigue' score at each scheduled assessment during Treatment and Observation Periods
- Change from Baseline in the MG Symptoms PRO 'Bulbar symptoms' score at each scheduled assessment during Treatment and Observation Periods

- Change from Baseline in the MG Symptoms PRO ‘Respiratory symptoms’ score at each scheduled assessment during Treatment and Observation Periods
- Change from Baseline in the MG Symptoms PRO ‘Ocular symptoms’ score at each scheduled assessment during Treatment and Observation Periods
- Change from Baseline in revised 15-item MG Quality of Life (MG-QoL15r) questionnaire at each scheduled assessment during Treatment and Observation Periods
- Change from Baseline in 5-Level European Quality of Life 5 Dimensions (EQ-5D-5L) scores at each scheduled assessment during Treatment and Observation Periods

For study participants who require rescue treatment during the Observation Period of MG0003 or MGC0003 and subsequently enter MG0004, the following endpoints will be assessed:

- QMG responder rate (≥ 3.0 point improvement from Baseline) at each scheduled assessment during the first 6 weeks of the Treatment Period
- MG-C responder rate (≥ 5.0 point improvement from Baseline) at each scheduled assessment during the first 6 weeks of the Treatment Period
- MG-ADL responder rate (≥ 2.0 point improvement from Baseline) at each scheduled assessment during the first 6 weeks of the Treatment Period

2.2.3 Pharmacokinetic, and pharmacodynamic

2.2.3.1 Pharmacokinetic endpoints

- Plasma concentration of rozanolixizumab at each scheduled assessment during the Treatment and Observation Periods

2.2.3.2 Pharmacodynamic endpoints

- Change from Baseline in total IgG and IgG subclasses at each scheduled visit
- Change from Baseline in MG-specific autoantibodies at each scheduled visit

2.2.4 Anti-drug antibody endpoints

- ADAs at each scheduled assessment during the Treatment Period and Observation Periods

2.2.5 Immunological endpoints

- Change from Baseline in serum complement levels (C3 and C4) and plasma complement levels (C3a and C5a) at each scheduled assessment during Treatment Period
- Change from Baseline in serum cytokines at each scheduled assessment during Treatment and Observation Periods
- Change from Baseline in serum immunoglobulin concentrations (total IgA, IgE, and IgM) at each scheduled assessment during Treatment and Observation Periods
- Change from Baseline in anti-tetanus toxoid serum titers at each scheduled assessment during Treatment and Observation Period

2.2.6 Other endpoints

- Dose change in use of concomitant medications during Treatment and Observation Period (See [Section 3.9](#))

- Change from Baseline in average daily dose (ADD) of concomitant medications (See [Section 3.9](#))

2.3 Study design and conduct

This is a randomized, open-label Phase 3 extension study to evaluate the long-term safety, tolerability, and efficacy of rozanolixizumab (RLZ) in study participants with generalized MG.

Study participants will enter MG0004 from lead-in study MG0003. Study participants in MG0003 who complete the Observation Period or who require rescue medication during the Observation Period will be invited to be rerandomized in MG0004 (except for study participants who opt to receive IVIg or PEX as rescue medication). Study participants who receive IVIg or PEX as rescue therapy during the Observation Period of MG0003 will not be eligible to enroll in MG0004. Study participants who discontinue study medication in MG0003 for any reason other than requiring rescue medication will not be eligible for MG0004.

For any study participant who enrolls in MG0004, the final visit in MG0003 (Visit 14) will serve as the first visit in MG0004 (Visit 1). All activities should be completed at Visit 1 (± 1 week). For criteria pertaining to laboratory measures, the last available value from MG0003 will be used for evaluation of study participant eligibility, as long as the measurement was taken within the last 4 weeks (not older than 32 days) prior to MG0004 Screening. Up to approximately 276 study participants will be enrolled into the lead-in study MG0003. All eligible study participants from MG0003 will be invited to participate in MG0004.

In MG0004, study participants will be randomized in a 1:1 ratio to receive 1 of 2 doses of rozanolixizumab (equivalent to approximately [REDACTED], respectively). Specifically, the following dose arms will be used in the study:

Dose arm 1: equivalent to approximately [REDACTED] rozanolixizumab

- Bodyweight <50kg: dose to be administered [REDACTED]
- Bodyweight ≥ 50 kg and <70kg: dose to be administered [REDACTED]
- Bodyweight ≥ 70 kg and <100kg: dose to be administered [REDACTED]
- Bodyweight ≥ 100 kg: dose to be administered [REDACTED]

Dose arm 2: equivalent to approximately [REDACTED] rozanolixizumab

- Bodyweight <50kg: dose to be administered [REDACTED]
- Bodyweight ≥ 50 kg and <70kg: dose to be administered [REDACTED]
- Bodyweight ≥ 70 kg and <100kg: dose to be administered [REDACTED]
- Bodyweight ≥ 100 kg: dose to be administered [REDACTED]

If one of the doses described above is determined to be discontinued after the interim analysis in MG0003, then that dose arm will be dropped from MG0004 as well, and study participants in the affected dose arm will be transferred to the continuing dose arm. If both dose arms are used in MG0004, study participants will be allowed to switch dose arms for tolerability and efficacy reasons at the discretion of the Investigator.

In MG0004, rozanolixizumab will be administered sc on a [REDACTED] basis over a 52-week Treatment Period. At the end of the 52-week Treatment Period in MG0004, study participants will participate in an 8-week Observation Period. The maximum study duration per study participant is 60 weeks.

This open-label extension (OLE) study will be replaced by MG0007, an OLE study with [REDACTED] based on MG worsening. Upon study site approval of MG0007, as well as fulfilment of regulatory requirements, study participants will have the opportunity to rollover directly into MG0007 and will no longer have the opportunity to rollover to MG0004. In the event a study participant has already started MG0004, a minimum treatment duration of 6 visits must be completed (if IMP treatment is withheld for low IgG, study participants missed dose(s) can be counted as part of the total 6 visits for completion of MG0004 and meet eligibility requirements for MG0007) and then the participant will discontinue MG0004 and have the opportunity to enter into MG0007. For study participants entering MG0007, he/she must complete the Premature End of Treatment (PEOT) Visit in MG0004 which will serve as the Screening Visit for MG0007 or as the End of Study (EOS) Visit for MG0004. If a study participant completes the Treatment Period and still in Observation Period of MG0004, he/she will then complete EOS Visit to serve as the Screening Visit for MG0007. Once the site is active for MG0007, no further participants will enroll in MG0004 and the study will be closed at the site once all eligible study participants have rolled over into MG0007.

A schematic of the study design is provided in Figure 2-1.

Figure 2-1: Study schematic

2.4 Determination of sample size

No formal sample size calculation can be performed. Up to approximately 240 study participants will be enrolled into the lead-in study MG0003. All eligible study participants from MG0003 will be invited to participate in MG0004 until study site approval of MG0007 as well as fulfilment of regulatory requirements.

3 DATA ANALYSIS CONSIDERATIONS

3.1 General presentation of summaries and analyses

Statistical analysis and generation of tables, figures, participant data listings, and statistical output will be performed using SAS[®] Version 9.3 or higher. All tables and listings will use Courier New font size 9.

Descriptive statistics will be displayed to provide an overview of the study results. For continuous variables, descriptive statistics will include number of participants with available measurements (n), mean, standard deviation (SD), median, minimum, and maximum.

For categorical variables, the number and percentage of participants in each category will be presented. Unless otherwise noted, the denominator for percentages will be based on the number of participants included in the respective analysis set. Participants with missing data can generally be accounted for using the following approaches:

- For summaries of demographics and Baseline characteristics: summarize percentages based on all participants in the analysis set and include a “Missing” category (corresponding to participants with missing data for the variable being summarized) as the last row in the list of categories being summarized.
- For summaries of efficacy and safety endpoints, unless otherwise specified: summarize percentages based only on those participants with observed data for the variable being summarized. As the denominator may be different from the number of participants in the analysis set being considered, the denominator should be displayed in the table. The general format for displaying this will be “n/Nsub (%)”.

Unless otherwise noted, all percentages will be displayed to one decimal place. No percentage will be displayed for zero counts, and no decimal will be presented when the percentage is 100%.

For PK concentration data, summary statistics will include geometric mean, geometric coefficient of variation (geoCV), 95% confidence intervals (CIs) for geometric mean, arithmetic mean, SD, median, minimum, and maximum.

Decimal places for descriptive statistics will always apply the following rules:

- “n” will be an integer;
- Mean (arithmetic, geometric), SD, and median will use one additional decimal place compared to the original data;
- geometric CV [%] will be presented with one decimal place;
- Minimum and maximum will have the same number of decimal places as the original value.

If no participants have data at a given visit, for example, then only n=0 will be presented. However, if $0 < n < 3$, present the n, minimum and maximum only. If n=3, n, mean, median, minimum and maximum will be presented only. The other descriptive statistics will be left blank.

Derived variables in general will display the mean and median to 1 more decimal place, SD to 2 more decimal places and same decimal place to minimum and maximum than the variables used

in the derivation. If the number of decimal places reported in the raw data is varied, then use either the maximum raw number of reported decimal places or 3, whichever is the lowest, as a guide for the descriptive statistics.

3.2 General study level definitions

3.2.1 Analysis time points

All data will be analyzed based on the visits identified per the Schedule of Activities in protocol. Mapping to analysis visit windows is not applied, except for PEOT visit (see [Section 3.2.3](#)).

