4.4 End of study definition

A participant is considered to have completed the study if he/she has completed all phases of the study including the End of Study (EOS) Visit (Week 60; see Section 1.3). The end of the study is defined as the date of the last visit of the last participant in the study. The maximum study duration per study participant is 60 weeks.

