7.2 Participant discontinuation/withdrawal from the study

Study participants are free to withdraw from the study at any time, without prejudice to their continued care.

A study participant may also be withdrawn at any time at the discretion of the Investigator for safety, behavioral, compliance, or administrative reasons.

If the participant withdraws consent for disclosure of future information, the Sponsor may retain and continue to use any data collected before such a withdrawal of consent.

If a participant withdraws from the study, he/she may request destruction of any samples taken and not tested, and the Investigator must document this in the site study records.

See the Schedule of Activities (Section 1.3) for data to be collected at the time of study discontinuation and follow-up and for any further evaluations that need to be completed.

Study participants **must** be withdrawn from the study if any of the following events occur:

1. Study participant withdraws his or her consent.
2. The Sponsor or a regulatory agency requests withdrawal of the study participant.
3. Study participant becomes pregnant during the study, as confirmed by a positive pregnancy test.
4. Study participant has active suicidal ideation as indicated by a positive response (Yes) to either Question 4 or Question 5 of the "Since Last Visit" version of the C-SSRS. The study participant should be referred immediately to a mental healthcare professional.

Study participants who withdraw from the study or discontinue study medication during the Treatment Period should complete the assessments outlined for premature end of treatment (PEOT) visit and enter the Observation Period.

Study participants who withdraw for any reason will not be eligible to participate in the managed access program.

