3.2.2 Study periods

The maximum duration of the study per participant will be approximately 60 weeks, consisting of the following 2 periods:

- Treatment Period: 52 weeks
- Observation Period: 8 weeks

The end of the study is defined as the date of the last visit of the last participant in the study.

The following definitions for starting and entering the study periods will be applied:

- **Treatment Period** starts with the first day of IMP in MG0004 and ends after Week 52 or PEOT assessments. All participants in the Safety Set will be considered to have started the Treatment Period. A participant is considered to have completed the Treatment Period if assessments from Treatment Period Week 52 are completed.
- **Observation Period** starts with one day after the end of the Treatment Period and ends after the final assessments at the End of Study (EOS) visit. Participants with assessment on any Observation Period day are considered to have started the Observation Period. Participants who complete the assessments at the EOS visit will be considered to have completed the

Observation Period. Participants who have a completed status in the study termination case report form (CRF) are considered to have completed the Treatment and Observation Period.

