3.2.3 Mapping of assessments performed at Premature End of Treatment Visit

PEOT assessments will be assigned to the next scheduled site visit (following the last scheduled visit that the participant completed prior to PEOT) where each assessment is evaluated as per protocol. This approach means that there is a chance that PEOT data will be mapped to different visits according to the schedule of assessments.

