10.2 Pharmacodynamics

10.2.1 Total serum IgG and IgG subclasses

Total serum IgG concentrations and IgG subclasses will be summarized by first dose received and time point for observed values, change from Baseline, and percentage change from Baseline.

The maximum change from Baseline in total serum IgG (absolute and percentage change) will be reported in the listing and summarized by first dose received. In the event that a change from Baseline in total serum IgG is not observed in a given participant, the maximum change will be reported as the smallest increase from Baseline.

Mean and mean percentage change from Baseline values in total serum IgG will be plotted over time by first dose received with dose groups overlaid on the same plot.

Spaghetti plots will be provided for absolute IgG and percentage change from baseline in IgG over time stratified by first dose received and Baseline bodyweight group (<50kg, 50kg-<70 kg, 70-<100kg, ≥100kg) where the Baseline bodyweight group is multipaneled or overlaying with different colors within each treatment group.

Serum concentrations of total IgG and IgG subclasses will be listed together with concentrations of rozanolixizumab, ADA and NAb sample status and titer, MG-specific autoantibodies, and MG-ADL change from Baseline, as specified in [Section 10.3.2](#).

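### The EOS visit has no analysis-visit rule, so the last by-visit row or point pools Week 60 completers with early stoppers seen from about Week 9-10

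*SAP*

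**What the plan says.** **Visit rule.** SAP 3.2.1: "All data will be analyzed based on the visits identified per the Schedule of Activities in protocol". It then adds: "Mapping to analysis visit windows is not applied, except for PEOT visit". SAP 3.2.3 supplies the PEOT rule: "PEOT assessments will be assigned to the next scheduled site visit", taken separately for each assessment. Neither section has a rule for EOS.

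**When EOS falls.** Protocol 4.4 defines study completion as all phases, "including the End of Study (EOS) Visit (Week 60; see Section 1.3"). Table 1-1 has one EOS column, Visit 53, headed Week 60.

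**Early stoppers.** Under Protocol 7.2, those who stop study medication during treatment "should complete the assessments outlined for premature end of treatment (PEOT) visit and enter the Observation Period". SAP 3.2.2 gives "Treatment Period: 52 weeks", then 8 weeks of observation that begins the day after Week 52 or PEOT and ends at EOS.

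**Transfer to MG0007.** Protocol 4.1 lets the PEOT visit double as EOS for those who transfer from the Treatment Period. For the others, SAP 2.3 says: "If a study participant completes the Treatment Period and still in Observation Period of MG0004", the EOS visit becomes the MG0007 Screening Visit. Neither document says whether that EOS may be brought forward.

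**Outputs.** SAP 9.1 summarises MG-ADL, MG-C and QMG by scheduled visit. SAP 10.2.1: "Mean and mean percentage change from Baseline values in total serum IgG will be plotted over time by first dose received". In SAP 10.3.2 the scatter plots of MG-ADL and IgG change against ADA titre name Week 60 as the last point, while other ADA figures use EOS. SAP 10.3.1 lists Week 60 and EOS as separate items.

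**The concern.** The column before EOS in Table 1-1 serves both Week 52 and PEOT. The SAP saw the problem there and moves early PEOT results to the next due site visit. The EOS column has the same problem and no rule. Early stoppers are thus largely taken out of Week 52 and then reappear in the Week 60 visit.

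EOS is the only scheduled off-drug assessment after 52 weeks of treatment. Readers will use the step into it to judge whether effect is lost and whether IgG and autoantibodies recover. If the two visits hold different people with different exposure, part of that step may be a change of population. The number in the Week 60 row could even exceed the number at Week 52, and the participant count by visit (SAP 5.1) would show the same distortion.

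**Working it through.** **Inputs**
- Treatment Period 52 weeks, Observation Period 8 weeks (SAP 3.2.2).
- Weekly visits, Visit k at Week k up to Visit 52 (Protocol 4.1, Table 1-1).
- Dosing interval: redacted. Weekly is assumed, in line with weekly visits and the top infusion-count category of 49-52 in SAP 8.1.
- PEOT at the next weekly visit after the last dose: assumed.

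**The plan's own figure.** Completer: 52 + 8 = Week 60. This reproduces Protocol 4.4.

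**Early stopper, last dose at Visit k.** EOS week = k + 8 counted from last dose, or k + 1 + 8 counted from PEOT. Gap to the nominal week = 60 minus that.

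| Last dose | EOS week (from last dose / from PEOT) | Weeks before Week 60 |
|---|---|---|
| Visit 1 | 9 / 10 | 51 / 50 |
| Visit 6 | 14 / 15 | 46 / 45 |
| Visit 12 | 20 / 21 | 40 / 39 |
| Visit 26 | 34 / 35 | 26 / 25 |
| Visit 40 | 48 / 49 | 12 / 11 |
| Visit 51 | 59 / 60 | 1 / 0 |

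**One participant traced through the MG-ADL table.** The last dose and last completed visit are Visit 12. The PEOT score goes to Visit 13, the next site visit with MG-ADL. The participant is absent from later rows, including Week 52. The EOS score, taken at Week 20-21, then enters Visit 53, nominally Week 60.

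**How far the row could drift in time (illustration only).** Let f be the share of early stoppers in the EOS row, with last dose spread evenly over Weeks 1 to 51. Their mean EOS week counted from PEOT is 26 + 1 + 8 = 35. The row's mean actual week is 60(1 - f) + 35f:
- f = 5%: 58.8
- f = 10%: 57.5
- f = 25%: 53.8
- f = 50%: 47.5

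If all early stoppers had EOS at Week 20, the corresponding means are 58.0, 56.0, 50.0 and 40.0. The documents give no value for f. Transfers to MG0007 during treatment have no separate EOS. This removes potential completers from the row and raises f.

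**Which outputs.** Table 1-1 collects MG-ADL, QMG, MG-C, IgG, autoantibodies, ADA, IgA/IgM/IgE and tetanus titre at EOS. Tetanus titre is not scheduled at Week 52, and IgA/IgM/IgE is taken there only for a PEOT visit. For these the affected step runs from the last on-treatment sample instead.

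**The case against.** **A reader might infer that every EOS result is shown as Week 60 and that the last row of every table is wrong.** The documents do not support that. SAP sections 9, 10.2 and 10.4 refer only to visits or time points, and the table shells that would fix the row label are not available. The Week 60 label is inferred from Table 1-1 and Protocol 4.4, except in the SAP 10.3.2 scatter plots, which name it. EQ-5D-5L, MGII, PK, complement and cytokines are not collected at EOS. Completers do attend at Week 60, so the row is not only Week 60, rather than not Week 60 at all. The pooling itself does not depend on the label.

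**Pooling at EOS is defensible.** Protocol 4.2 chose 8 weeks as the expected time for antibodies to return to Baseline. On the timing above, early stoppers and completers are both about 8 weeks off drug. This stands: such a summary is legitimate if it is labelled as time since end of treatment. It is not a Week 60 result after long-term treatment, since prior exposure may be a single dose.

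**Early stoppers might attend at calendar Week 60.** Protocol 7.1.1 and 7.1.2 tell some of them to follow the visit schedule. Week 60 would then be right by calendar, but someone with one dose at Week 1 would be 60 - 1 = 59 weeks off drug, beside completers at about 8 weeks. Either reading leaves an undefined mixture.

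**Much is already visible, and nothing is tested.** Listings give days since last infusion (SAP 3.2.1.1), each row shows n, and observed-case rows always differ in membership. This is fair mitigation, but listings do not correct the tables or mean plots, and these descriptive summaries are the only planned efficacy and PD results.

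**Conclusion.** The point holds for assessments collected at EOS and summarised or plotted by visit. With no rule for EOS, the last nominal visit pools completers at Week 60 with early stoppers seen from about Week 9-10. It may also include participants whose EOS was brought forward for MG0007, with less than 8 weeks of observation; that is one reading of SAP 2.3, not a stated rule.

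The timing rests on weekly dosing and on the 8-week Observation Period running from PEOT or last dose. A single result can sit 50-51 weeks from its nominal week. The effect on any mean is unknown, because the documents give neither discontinuation nor completion rates. A reader might be tempted to state a shift in MG-ADL points; that would need a between-group difference the documents do not contain.

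The primary endpoint is not affected, because TEAEs are assigned by date. This is a gap in the SAP that should be closed before the by-visit tables are produced, not a threat to the study's main safety conclusions.

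**What to change.** Add to SAP 3.2.1:
- EOS results are reported and plotted as Week 60 only for participants who completed the Week 52 visit and attended EOS at its scheduled time, about 8 weeks after the Week 52 visit, whatever the date of last dose.
- All other EOS results go in a separate row, 'EOS outside Week 60 (early stop or early EOS)', with study week and days since last dose. They are not plotted at Week 60.
- If an all-participant row is kept, it is labelled 'EOS (about 8 weeks after end of treatment)'.

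The rule should be tied to the Week 52 visit and not to a window of days since last dose. Dosing can be paused while visits continue (Protocol 6.5.3 and 7.1.4). A completer whose last dose was at Week 48 is (60 - 48) x 7 = 84 days off drug at a genuine Week 60 visit, and a narrow days-off-drug window would wrongly exclude that result.

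Cost: a short addition to the SAP, one extra row per affected table, and fewer participants in the Week 60 row. No new data are needed.
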